9.2 Protocol deviations	

1 INTRODUCTION

1.1 Study Objectives

	• To actimate the offect of dependifications placebology (and 1)	
Primary Study • To estimate the effect of dapagliflozin vs. placebo on 6- ar week NT pro-BNP.		
Objectives	 To compare the proportion of patients that achieve a meaningful change from baseline in quality of life (≥ 5-point increase in average of 6- and 12-week KCCQ overall summary scores) or NT pro-BNP (≥ 20% decrease in average of 6- and 12-week NT pro-BNP) between dapagliflozin and placebo. 	
Secondary Study Objectives	 To compare the proportion of patients with a ≥ 5-point increase in the average of 6- and 12-week Kansas City Cardiomyopathy Questionnaire (KCCQ) scores, from baseline, between dapagliflozin and placebo. To compare the proportion of patients with a ≥ 20% decrease in the average of 6- and 12-week NT pro-BNP, from baseline, between dapagliflozin and placebo. To compare the proportion of patients with both a ≥ 5-point increase in the average of 6- and 12-week KCCQ overall summary scores and a ≥ 20% decrease in the average of 6- and 12-week KCCQ overall summary scores and a ≥ 20% decrease in the average of 6- and 12-week NT pro-BNP, from baseline, between dapagliflozin and placebo. To estimate the effect of dapagliflozin vs. placebo on 6- and 12-week NT pro-BNP. To estimate the effect of dapagliflozin vs. placebo on 6- and 12-week BNP. To estimate the effect of dapagliflozin vs. placebo on 6- and 12-week BNP. To estimate the effect of dapagliflozin vs. placebo on 6- and 12-week HbA1c (evaluated separately in patients with and without type 2 diabetes). To estimate the effect of dapagliflozin vs. placebo on 6- and 12-week weight. To estimate the effect of dapagliflozin vs. placebo on 6- and 12-week systolic blood pressure. 	
Exploratory objectives	 To estimate the effect of dapagliflozin vs. placebo on daily loop diuretic dose (furosemide equivalent). To estimate the effect of dapagliflozin vs. placebo on hospitalizations for heart failure. To estimate the effect of dapagliflozin vs. placebo on urgent outpatient heart failure visits. To estimate the effect of dapagliflozin vs. placebo on hospitalizations for heart failure or urgent outpatient heart failure visits. To estimate the effect of dapagliflozin vs. placebo on hospitalizations for heart failure or urgent outpatient heart failure visits. To compare the change in NYHA Class from baseline at 6 and 12 weeks between dapagliflozin and placebo. 	

1.2 Study Design

Design Configuration and Subject Population	 A 12-week randomized, double-blind, placebo-controlled trial to evaluate the effects of once-daily dapagliflozin 10 mg on heart failure disease-specific biomarkers (BNP and NT pro-BNP), symptoms, health status, and quality of life in patients with type 2 diabetes and chronic heart failure with reduced systolic function. Substudies will also be conducted for exploratory biomarker analyses and effects on arrhythmia burden.
Treatment Groups	Dapagliflozin 10 mg administered orally vs. placebo
Inclusion criteria	 Age > 18 and < 120 at the screening visit Established diagnosis of heart failure (for at least 16 weeks prior to the screening visit) with reduced systolic function (LVEF≤40% due to either ischemic or non-ischemic etiology) documented by an imaging modality (echocardiography, nuclear imaging, LV angiography, magnetic resonance imaging) within the past 24 months. Any local measurement of LVEF by any modality within the eligibility range made within the past 24 months is acceptable provided there has been no subsequent LVEF measurement above 40%. No change in diuretic management for 1 week prior to screening visit or between the screening and randomization visit NYHA class II or III heart failure symptoms at the screening and randomization visit BNP ≥100 pg/mL and/or NT pro-BNP ≥ 400 pg/mL at the screening visit (For patients with permanent atrial fibrillation inclusion thresholds will be BNP ≥ 125 pg/mL or NTproBNP ≥ 600 pg/mL) Ability to provide informed consent prior to initiating screening visit procedures
Exclusion criteria	 Decompensated heart failure (hospitalization for heart failure within the 30 days prior to screening or NYHA class IV heart failure symptoms at screening) History of type 1 diabetes Estimated glomerular filtration rate (eGFR) < 30 at the screening visit by modified MDRD equation GFR in mL/min per 1.73 m² = 175 x SerumCr^{-1.154} x age^{-0.203} x 1.212 (if patient is African American) x 0.742 (if female) Admission for an acute coronary syndrome (ST-elevation MI, non-ST-elevation MI, or unstable angina), percutaneous coronary intervention, or cardiac surgery within 30 days prior to the screening visit.

I	
	 Admission for cardiac resynchronization therapy (CRT) within 90 days prior to the screening visit Planned cardiovascular revascularization (percutaneous intervention or surgical) or major cardiac surgery (coronary artery bypass grafting, valve replacement, ventricular assist device, cardiac transplantation, or any other surgery requiring thoracotomy) or CRT within the 90 days after the screening visit. Participation in any interventional clinical trial (with an investigational drug or device) that is not an observational registry within the 8 weeks prior to the screening visit. History of hypersensitivity to dapagliflozin For women of child-bearing potential: Current or planned pregnancy or currently lactating. Women who are surgically sterile or those who are postmenopausal for at least 1 year are not considered to be of child-bearing potential. Women of child-bearing potential, who are sexually active, must agree to use a medically- accepted method of birth control for the duration of the study. Acceptable birth control methods include: (1) surgical sterilization (such as a hysterectomy or bilateral tubal ligation), (2) progesterone hormonal contraceptives (birth control pills or implants), (3) barrier methods (such as a condom or diaphragm) used with a spermicide, or (4) an intrauterine device (IUD). Women of child-bearing potential will have a urine pregnancy test at every clinic visit and it must be negative to continue study participation. Life expectancy <1 year at the screening visit
	 examination at the time of the screening or randomization visit BNP <100 pg/mL and NT pro-BNP<400 pg/mL at the screening visit (For patients with permanent atrial fibrillation exclusion thresholds will be BNP<125 pg/mL and NTproBNP<600 pg/mL) Patients currently being treated with any SGLT-2 inhibitor (dapagliflozin, canagliflozin, empagliflozin) or having received
	 treatment with any SGLT-2 inhibitor within the 12 weeks prior to the screening visit. Average supine systolic BP <90 mmHg at the screening or randomization visit
	 Past or current history of bladder cancer Active Hematuria Donation of blood or bone marrow 12 weeks prior to the
	 screening visit and no planned donations during the study period Heart failure due to restrictive cardiomyopathy, active myocarditis, constrictive pericarditis, severe stenotic valve disease, and HOCM (hypertrophic obstructive cardiomyopathy).

1.3 Sample Size and Power

Planned Sample Size	• Approximately 110 patients will be enrolled in each arm.
Power Statement	• The first dual primary endpoint of this study is the average of 6- and 12- week NT pro-BNP. A generalized linear mixed model with patient as a random effect will be used to estimate the average effect over 6 and 12 weeks controlling for baseline NT pro-BNP and other pre-specified covariates. A gamma distribution with log link will be used to account for the skewed nature of NT pro-BNP. Several sensitivity analyses will be performed, one of which includes site as a random effect to account for clustering of patients within centers. For the first dual primary endpoint a sample size of 110 for each group will achieve 80% power with α =0.05 to detect a difference in NT pro-BNP between the two groups of at least 302 pg/mL from baseline to 12 weeks. The assumptions for this calculation were derived from the BATTLESCARRED trial where the estimated standard deviation for NT pro-BNP was 1250 pg/mL. We expect the standard deviation in the DEFINE-HF Trial to be somewhat lower (961 pg/ml) given lower NT pro-BNP threshold. Of note, 302pg/mL reduction in NT pro-BNP is equivalent to 31.5% of the standard deviation in NT pro-BNP (based on the above assumption). There is an anticipated non-completion rate of approximately 13% so the final sample size per group will be 125.
	 The second dual primary endpoint, the proportion of patients with a ≥ 5-point KCCQ overall summary score increase or a ≥ 20% decrease in NT pro-BNP, averaging over 6 and 12 weeks, will be analyzed using generalized linear mixed models controlling for baseline NT pro-BNP and KCCQ overall summary score as well as several additional covariates as specified below. A binomial distribution with logit link will be used. Several sensitivity analyses will be performed, one of which includes site as a random effect to account for clustering of patients within centers. Power was determined based on comparisons of proportions between two independent groups, where the anticipated control group percent change is 30%. A sample size of 110 for each group will achieve 80% power with α=0.05 to detect an absolute difference in proportions between the two groups of 18% from baseline to 12 weeks for the second dual primary endpoint.

1.4 Substudies

Substudies	• Arrhythmia Substudy: Patient participation will be optional. At the screening visit, those likely to be enrolled will be given the option to participate in the arrhythmia substudy. If they elect to enroll they will wear a Holter monitor for 14 days to establish a baseline. The 14-day Holter will be repeated at the 6-week visit to compare change in arrhythmia burden. Outcomes of VT, NSVT episodes, VF, A fib, and PVCs will be compared between dapagliflozin and placebo.
	• SensiVest Substudy: Patients at selected sites who elected to participate will have blinded lung fluid volume measurements at rest during the randomization (week 0), 6, 12 and 13 week visits. Lung fluid volume will be compared between the treatment group and placebo group over the 12 weeks of treatment.
	• Biomarker Substudy : A biomarker substudy will be conducted. Specimens will be collected for exploratory biomarker testing from patients at the Randomization, Week 6 and Week 12 visits to assess the impact of dapagliflozin versus placebo on known markers of myocardial fibrosis/necrosis, inflammation, and oxidative stress.

2 GENERAL CONSIDERATIONS FOR DATA ANALYSES

2.1 Analysis Data Sets

Efficacy and safety analyses will be performed on data from the following analysis sets:

- Enrolled patients set (EPS) will consist of all patients who signed the informed consent. This data set will be used to summarize the patient disposition data.
- Modified intention to treat set (modified ITTS) is defined as all patients who have been randomized to study treatment, have received at least one dose of study medication, and have sufficient evaluable data for endpoint ascertainment during follow up. For clarity, patients with no evaluable data for a particular outcome during follow up will be excluded from the analyses of these respective endpoints. In patients who undergo initiation of intravenous home inotropic support and/or receive left ventricular assist device or heart transplant during the study or who are started on a prohibited medication (open label SGLT-2is), for efficacy analyses, the last available data point(s) prior to these events will be used. Subjects will be analyzed according to the randomization group. The modified ITTS data set will be used for the primary, secondary, and selected exploratory (NYHA class, loop diuretic dose) efficacy endpoints.
- On-treatment set (OTS) includes all subjects in the modified ITTS. Primary and secondary endpoint measurements will be excluded for the follow-up time point(s) when subjects were temporarily or permanently off the study drug at the time the corresponding measurements were obtained. The OTS data set will be used for a sensitivity analyses for the primary, secondary, and selected exploratory (NYHA class, loop diuretic dose) efficacy endpoints.
- The per protocol set (PPS) includes all subjects in the modified ITTS who did not have any major protocol deviations. Major protocol deviations, which are detailed in section 2.2, will be determined prior to unblinding of treatment groups. Subjects will be summarized according to actual treatment received regardless of the allocated treatment. This will be used for a sensitivity analysis for the primary efficacy endpoints only.
- The safety analysis set (SAFS) includes all patients who received at least 1 dose of study medication. Throughout the safety results sections, erroneously treated patients (eg, those randomized to dapagliflozin but actually given placebo) will be accounted for in the actual treatment group. If a patient received study drug from the wrong kit for only a part of the treatment duration and then switched to another, the associated actual treatment group for that patient will be the treatment group the patient had the longest exposure to. The main safety analyses will be restricted to adverse events that occurred between randomization and the 12-week visit. Adverse events that occurred between 12 weeks and 13 weeks (after discontinuation of study treatment) will be collected, and presented in a separate, supplemental analysis. The safety analysis set will be used to summarize safety data and patient demography and their baseline characteristics, and to analyze selected exploratory endpoints (heart failure hospitalizations, urgent heart failure visits, and a composite of heart failure hospitalizations or urgent heart failure visits). If there is a difference between the SAFS and modified ITTS, baseline and demography data will also be presented for the IITS.

2.2 Protocol Deviations and Major Eligibility Violations

Important Protocol Deviations (IPDs) are defined as those important deviations from the protocol that are likely to have an impact on the efficacy and/or safety of study treatments.

Protocol deviations will be reviewed in a blinded fashion by the study team prior to database lock. All decisions to exclude patients and/or data from the modified ITTS or PPS will be made prior to the unblinding of the study and agreed by the study team.

Error! Reference source not found.9.2 specifies the criteria for IPDs Patients having IPDs will be summarized and listed by treatment group and overall. The list of protocol deviations (including IPDs) will be compiled separately and finalized prior to database lock.

2.3 Strata, Covariates, and pre-specified subgroup analyses

All efficacy and safety endpoints will be analyzed in the entire cohort, and then within the subgroups of patients with and without diabetes. Analyses for the primary and secondary endpoints will be adjusted for the corresponding baseline measurements as well as history of diabetes (DM), eGFR, and age. A sensitivity analysis will be conducted for each endpoint adjusting for the following additional baseline covariates: AFib type (No AFib, persistent/permanent AFib, paroxysmal AFib) and LVEF (as continuous variable). Restricted cubic splines will be used for continuous variables to accommodate non-linear effects.

Additional sensitivity analysis will repeat the primary analysis but will also include site as a random effect to account for potential clustering by enrolling center. A different sensitivity analysis will use the same model as the primary analysis, but adjust only for the corresponding baseline measurements, without additional covariates.

Additionally, the following pre-specified subgroup analyses will be performed for the primary endpoints (stratified by the baseline variables below):

- Baseline NTproBNP (< median, ≥ median)
- Baseline LVEF (≤30%, > 30%)
- Atrial fibrillation type (No AFib, permanent/persistent AFib, paroxysmal AFib)
- Baseline KCCQ overall summary score (<70, ≥70)
- Baseline eGFR (<60, ≥60 mL/min/1.73 m²)
- Type of cardiomyopathy (ischemic, non-ischemic)
- Age (<65, ≥65)
- Sex (male, female)
- Race (white, black, other)
- Baseline RAASi type (ARNI, ACE/ ARB, neither)
- Loop diuretic dose (Furosemide equivalent mean daily dose: \leq 40 mg, >40 mg)

Subgroup analyses will be carried out by augmenting the primary analysis model with terms for subgroup and a subgroup-by-treatment interaction. Adjusted point estimates and 95% confidence intervals will be calculated for the effect of dapagliflozin compared with placebo within each subgroup. An interaction p-value will be provided.

Due to the large number of study sites and the expected low number of patients per site, site effects will not be explored, although study site will be included as a random effect in efficacy sensitivity analyses to account for within-site correlations, as specified above.

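### Effect modification by six continuous or ordered baseline variables is tested only through two-group splits; adding a continuous interaction test would recover information if the modification is roughly linear

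*SAP*

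**What the plan says.** SAP 2.3 lists eleven subgroup factors for the two primary endpoints, in addition to the analyses by diabetes status. The model is stated as "Subgroup analyses will be carried out by augmenting the primary analysis model with terms for subgroup and a subgroup-by-treatment interaction". Adjusted estimates with 95% confidence intervals are given within each subgroup, and "An interaction p-value will be provided".

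Six of the eleven factors are measured on a continuous or ordered scale and cut into two groups:

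- NT-proBNP at the sample median: "Baseline NTproBNP (< median, ≥ median"
- LVEF at 30%: "Baseline LVEF (≤30%, > 30"
- KCCQ overall summary score at 70: "Baseline KCCQ overall summary score (<70, ≥70"
- eGFR at 60: "Baseline eGFR (<60, ≥60 mL/min/1.73 m²"
- age at 65
- loop diuretic dose at 40 mg furosemide equivalent per day

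No treatment interaction with the uncut variable is planned anywhere. SAP 5.4 allows the same strata to be reused for all secondary efficacy outcomes.

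For covariate adjustment the same section takes a different line: "Restricted cubic splines will be used for continuous variables to accommodate non-linear effects". SAP 5.1.1 adjusts the first primary endpoint for log baseline NT-proBNP, eGFR and age, and SAP 5.1.2 adds baseline KCCQ for the second. LVEF enters a sensitivity analysis as a continuous variable.

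**The concern.** The plan keeps the full scale of these variables when it adjusts for them and drops it only when it asks whether the treatment effect varies with them. For NT-proBNP, eGFR and age the continuous main effect is already in both primary models, so a product term with treatment is all that is missing.

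A two-group interaction test uses only which side of the cut a patient falls on. If the treatment effect changes gradually, the distance from the cut also carries information, and it is thrown away. The trial is sized for overall treatment effects (SAP 1.3), and no power is stated for any interaction. A further avoidable loss makes a non-significant interaction P value harder to interpret.

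The NT-proBNP cut has an additional weakness. Because it is the sample median, its value is unknown until the data are in, and it will not carry over to another trial. The other five cuts are fixed in advance.

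**Working it through.** **Plan's own figure.** There is none for subgroup interactions. The sample-size figures in SAP 1.3 concern overall effects and do not enter below, because the ratio calculated does not depend on the number of patients or on the outcome SD.

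**Method.** With randomised treatment and an interaction linear in a modifier X, the share of the interaction information kept by a two-group split is the squared correlation between X and the split indicator. For a normal X, with a share p of patients on one side of the cut and z_p the corresponding normal quantile:

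share kept = φ(z_p)² / [p(1 − p)]

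This is a linear-model result. It is an approximation for the gamma and logistic models in the SAP.

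**Inputs.** p = 0.5 for NT-proBNP, because the cut is the median. Normality of log NT-proBNP is an assumption, as is linear modification on that scale. The 30/70 share is an illustration; the documents give no split share for the other five variables.

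**Results, normal modifier.**

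- 50/50: 0.3989² / 0.25 = 0.637 kept, so 36% lost
- 30/70: 0.3477² / 0.21 = 0.576 kept, so 42% lost

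A simulation with 220 patients, a normally distributed outcome and the continuous main effect kept in the model gave losses of 36.5% at 50/50, 38.6% at 40/60 and 43.9% at 30/70.

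**Power.** Take an interaction that the continuous test would detect with 80% power at two-sided 0.05, so that the expected z is 1.960 + 0.842 = 2.802:

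- 50/50: Φ(2.802 × √0.637 − 1.960) = 61%
- 30/70: Φ(2.802 × √0.576 − 1.960) = 57%

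To regain 80% after splitting would take 1/0.637 = 1.57 or 1/0.576 = 1.74 times the patients.

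**Other distributions and splits (all assumed, none from the documents).**

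| Case | Information lost |
|---|---|
| Uniform modifier, 50/50 | 25% |
| Normal modifier, 20/80 | 51% |
| LVEF, truncated at 40% | 33–47% |
| KCCQ, cut at 70 | 34–36% |
| eGFR at least 30, cut at 60 | 39–44% |
| Age, cut at 65 | 38% |
| Loop diuretic dose in steps, with zeros | 28–31% |

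Truncation matters for LVEF because eligibility requires "reduced systolic function (LVEF≤40% due to either ischemic or non-ischemic etiology". Diuretic dose is not normal because SAP 2.4 codes non-users as 0 mg.

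**Scale.** If the modification were linear in raw rather than log NT-proBNP, an assumed lognormal distribution with log-SD 0.9 gives a 68% loss at the median. The log scale is used here because it is the one in the primary model.

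**Shape.** If the effect steps exactly at the cut, the split loses nothing, and a linear term would keep only 64% (50/50) or 58% (30/70). For S-shaped modification centred on a median cut, with a logistic slope of 2 per SD of the modifier, the split keeps 78% and a linear term 93%. At a slope of 4 the figures are 87% and 84%. A symmetric U-shape is missed by both a median split and a linear term.

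**The case against.** The strongest objection is to reading 36–42% as the loss for all six variables. The documents do not support that. The range needs a near-normal modifier, a linear interaction and a split no more uneven than 30/70, and only NT-proBNP has a known split share. This objection stands, and it limits the size that can be claimed.

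A reader might also infer that the continuous test is always the better one and should replace the planned P value. It is not always better, as the step case shows. A P value from the same model as the displayed subgroup estimates tests the contrast shown beside it; replacing it would break that link. This also stands, and it argues for adding a test.

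Nor can the two-group display be used to check linearity. Two estimates always lie on a straight line, so they cannot separate a gradual change from a step.

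A reader might infer that patients just either side of a cut are treated as prognostically different. For NT-proBNP, eGFR and age, and for KCCQ in the second endpoint, the primary model keeps the continuous main effect, so only the treatment interaction is cut in two.

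Finally, no interaction is powered, and the 80% starting point flatters the illustration. By the same formula, 20% power falls to about 14% at a median split, and either test would usually miss such an effect. That is fair, and it keeps the point minor. It does not remove the case for using information already collected.

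**Conclusion.** The point holds in a limited form. SAP 2.3 tests effect modification by six continuous or ordered variables only through two-group splits, although it already carries most of them as continuous covariates. If modification is roughly linear, the split costs about 36% of the interaction information for NT-proBNP (median cut, log scale, near-normal) and would cost 42% for a near-normal variable split 30/70. For LVEF, KCCQ, eGFR, age and diuretic dose the loss cannot be fixed from the documents; roughly a quarter to a half is a reasonable illustrative range. It is zero if the effect steps at the cut, but the documents give no reason to expect a step at any of the six cuts.

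The loss falls only on the subgroup interaction tests. The overall tests of the two primary endpoints do not change. This is a worthwhile refinement, not an error that threatens the trial's conclusions.

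**What to change.** Keep every listed subgroup, its estimates and confidence intervals, and its two-group interaction P value. Before unblinding, add to SAP 2.3, for each of the six variables and in the same model:

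1. A test of treatment by the uncut variable, using the log scale for NT-proBNP as in SAP 5.1.1 and stating the scale for each of the others. Add the variable's main effect where the model lacks it.
2. A restricted cubic spline version of the interaction, with the knots stated in advance, to check linearity. The knots need stating because SAP 2.3 gives none.
3. A plot of the estimated treatment effect, with its confidence band, against the variable.

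For loop diuretic dose, the mass at zero and a few high doses could drive a linear term, so the spline check and the plot matter most there.

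The cost is a short SAP paragraph and a few lines of code, with no new data. It brings six more exploratory P values per primary endpoint (6 × 2 = 12) plus the spline checks, all to be labelled exploratory. It also brings an assumption about shape, which the spline version can examine, though with limited power at this sample size.
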